### 4.3 Analysis

Overnight PSG will be performed at the WCMC Center for Sleep Medicine. Multichannel data acquisition equipment (Grass Technologies TWin PSG Clinical Software) will be used to record four channels of electroencephalography (O1/O2, C3/C4), chin electromyography, bilateral electrooculography, electrocardiogram, and anterior tibialis electromyography. Audio and video will be simultaneously digitally recorded. All PSG records will be manually scored and double-checked by analysts blind to the results of the devices being evaluated, using American Academy of Sleep Medicine criteria. Principal PSG outcome measures are sleep efficiency and total sleep time.

Analysis will be conducted by comparing data gathered by the consumer sleep monitoring device(s) against manually scored polysomnogram. Epoch-by-epoch data will be gathered into pooled contingency tables for analysis. Data will be analyzed according to several degrees of rigor:

Stage-by-stage (with N1 and N2 combined into Light)  
Wake / REM / NREM (with N1, N2, N3 combined into NREM)  
Wake / Sleep (with N1, N2, N3, and REM combined into Sleep)

Percent agreement, sensitivity, and specificity will be calculated for pooled epoch data (overall and for each stage: Wake, Light, Deep, and REM).

Cohen's kappa will be calculated. What kappa value is considered indicative of weak or strong correlation is subjective and different classifications have been proposed:

A kappa value of:

0 – 0.2 is considered essentially slight/no agreement  
0.2 – 0.4 is considered fair/low agreement  
0.4 – 0.6 is considered moderate agreement  
0.6 – 0.8 is considered substantial/high agreement  
0.8 – 1.0 is considered nearly perfect agreement

Agreement levels of several sleep metrics will be assessed using Intraclass Correlation Coefficients: Total Sleep Time (TST), Sleep Onset Latency (SOL), Latency to Persistent Sleep (LPS), Latency to REM (REML), Wake After Sleep Onset (WASO), Sleep Efficiency (SE), and time spent in particular sleep stages (Light, Deep, REM).

Positive Predictive Value (PPV) will be calculated for each stage type: Wake, Light, Deep, REM.

Data will be analyzed using SPSS software.

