### **REFERENCES**

## **1. OBJECTIVES**

### **1.1. Primary Objectives**

This study seeks to evaluate three new commercial sleep monitoring devices: Fitbit, Jawbone UP, and Microsoft Band by comparison against concurrent polysomnography (PSG) in a clinical population. The primary objective is to compare total sleep time (TST) between each of the sleep monitoring devices and PSG.

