## 2.3 Rationale and Background

The ability to investigate sleep is of scientific and clinical interest. Sleep patterns are studied with PSG, subjective self-reported diaries and questionnaires, and actigraphy. Each method of measuring sleep has advantages and limitations.

Historically, the gold standard of sleep measurement has been laboratory PSG, which utilizes a combination of electroencephalography (EEG), electrooculography, and electromyography (EMG) to determine sleep stages and sleep-related phenomena such as arousals. Laboratory PSG recordings require a physical space to conduct the sleep assessment and an on-site overnight staff to both apply and remove the physiological sensors and to ensure the integrity of acquired data. Data are often scored visually, in 30-second epochs, by registered PSG technicians. PSG boasts the advantage of excellence in terms of individualized sleep staging accuracy; however, the financial costs and time associated with conducting the data acquisition and subsequent scoring of the sleep records, as well as the burden to participants or patients, can outweigh this benefit. In those research studies and clinical screening applications in which in-home sleep monitoring over many days or weeks is required, the use of portable multichannel PSG is often financially and logistically impractical.

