The development of low-cost, portable, easy-to-use sleep recording devices, with automated algorithms to distinguish between sleep stages, has important implications for sleep medicine and research. Clinical validation using a large diverse population of participants will provide substantial insight into the accuracy of these new commercial sleep monitoring devices. This study follows a validation study (Protocol Title: Validation of a New Sleep Measurement Device / IRB Protocol Number 1210013184) of another consumer sleep monitoring device we conducted in 2014. This study provided a wealth of data and we are currently preparing to publish our results.

A recent validation study (Montgomery-Downs 2012) found Fitbit to have high sensitivity but poor specificity (tending to misidentify wake as sleep and thus overestimate total sleep time). The participants in this study (N=24) were healthy (non-disordered) young adults. The study concluded with a recommendation of additional validation using a clinical population of varying ages. A separate validation study (Zambotti 2015) found Jawbone UP likewise to have high sensitivity but low specificity in a population (N=28) of middle-aged females. Another validation study (Zambotti 2015) found Jawbone UP to have good agreement levels with PSG for total sleep time, sleep efficiency, and wake after sleep onset in a population of healthy adolescents (N=65). The study concluded with a recommendation that additional validation is needed in other age groups and clinical populations before advocating use of these inexpensive and easy-to-use devices in clinical sleep medicine and research. Our study will involve a diverse clinically relevant (referred for suspected sleep disorder, e.g., sleep apnea, hypersomnia, insomnia, restless leg syndrome) population of a wide age range (18-80). Our study will also involve a substantially larger sample size (N=100 per device). Lastly, we will use the latest available version of each device as design and detection / discrimination algorithms are continually evolved and refined.

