#### **4.2 Sample Size / Accrual Rate**

A total of 300 participants will be recruited (100 per device).

This number is based on several considerations. First, a similar sample size was used in previous validation studies of similar sleep monitoring devices: N=150 in our 2014 validation of Zeo Personal Sleep Coach (Protocol Title: Validation of a New Sleep Measurement Device / IRB Protocol Number: 1210013184), N=99 in Kaplan's 2014 validation of Zmachine, and N=65 in Zambotti's 2015 validation of Jawbone UP. In addition, this number is guided by logistical considerations of average laboratory throughput. Based on our experience, we realistically expect to recruit an average

of 5 participants per night, 30 participants per week, or 120 participants per month.

This sample size will allow us to describe the difference in total sleep time with a 95% confidence interval of +/-2.5 minutes, assuming a SD of 12.4 as was observed in a prior study of Fitbit.

The total number of complete data sets collected may be less than 300 as a participant may be unable to fall asleep while in the lab or may elect to end the study prematurely. However, the number of such eventualities should be low, e.g., < 5%. Participants with incomplete data will not be replaced.

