#### 4.4 Study Monitoring

The investigators will follow weekly accrual statistics including number of participants approached for participants, proportion giving consent, and reasons for refusal. We expect 20-30 participants to enroll per week. We expect to complete accrual in mid-2016.

We are not planning formal interim analyses. We will perform interim evaluation of study data after 10 participants have worn each device to assure that there are no issues with data transfer and to develop the detailed analysis plan. We do not expect any adverse events related to study participation. The investigators will review the occurrence of any device related adverse events. An outside review may be convened if the investigators are concerned about the occurrence of adverse events.

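### Section 4.3 does not carry through the TST difference and 95% CI on which section 4.2 sizes the study; the only statistic it ties to TST is an ICC of unstated form

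*Combined protocol and SAP*

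**What the plan says.** All references are to the combined protocol and SAP.

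- Section 1.1 sets the aim: "The primary objective is to compare total sleep time (TST) between each of the sleep monitoring devices and PSG".
- Section 4.2 justifies 100 participants per device by precision: "This sample size will allow us to describe the difference in total sleep time with a 95% confidence interval of +/-2.5 minutes". It assumes an SD of 12.4 from an earlier Fitbit study, expects fewer than 5% incomplete data sets, and does not replace them.
- Section 4.3 confirms the standing of TST: "Principal PSG outcome measures are sleep efficiency and total sleep time". It says in general terms that device data will be compared with the scored polysomnogram, without naming a statistic for that comparison.
- Section 4.3 then turns to epochs: "Epoch-by-epoch data will be gathered into pooled contingency tables for analysis". Percent agreement, sensitivity, specificity, kappa and positive predictive value follow.
- TST meets a named statistic in one sentence only: "Agreement levels of several sleep metrics will be assessed using Intraclass Correlation Coefficients: Total Sleep Time (TST", the first in a list of sleep metrics. The ICC model, the choice between consistency and absolute agreement, the unit and the interval are not stated. The graded bands in that section are for kappa.
- Section 4.4 plans a look at the data after 10 participants have worn each device, "to assure that there are no issues with data transfer and to develop the detailed analysis plan". That later plan is not in the documents.

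**The concern.** The quantity that sized the study and the quantity listed for analysis are not the same. Section 4.2 promises a difference in minutes with an interval. Section 4.3 lists an index without units. If section 4.3 were followed to the letter, the primary result for a device could be a single ICC, and its value would depend on which form the analyst selected in the software.

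The size and direction of the TST error are open questions here. Section 2.3 describes Fitbit in healthy young adults as "tending to misidentify wake as sleep and thus overestimate total sleep time". It reports low specificity for Jawbone UP in middle-aged women, but good TST agreement for the same device in healthy adolescents. A reader will want to know how many minutes each device is off in a clinical population, in which direction, and how much that varies between patients. An ICC answers none of these.

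Timing adds to the problem. If the gap is left to the detailed plan in section 4.4, the primary analysis would be settled after some of the study's data had been examined.

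**Working it through.** **1. The plan's own figure.** Inputs from section 4.2: SD 12.4 min (taken as the SD of the paired difference), n = 100 per device, up to 5% incomplete.

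Half-width = multiplier × SD / √n.

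| n | z (1.96) | t |
|---|---|---|
| 100 | 1.96 × 12.4 / 10 = 2.43 | 2.46 |
| 95 | 1.96 × 12.4 / 9.747 = 2.49 | 2.53 |

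The stated ±2.5 min reproduces. The target in section 4.2 is therefore the paired TST difference within one device group, and the arithmetic is sound.

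**2. What an ICC does with a bias.** Let device TST = PSG TST + b + e, with PSG TST of SD s and e of SD 12.4. Assumptions not in the documents: mean PSG TST 360 min, s = 60 or 80 min, b from 0 to 60 min. The average of the two variances is s² + 12.4²/2 = s² + 76.9. In large samples, single-measure forms:

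- consistency ICC = s² / (s² + 76.9)
- absolute-agreement ICC = s² / (s² + 76.9 + b²/2)

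| Constant b (min) | Consistency, s = 60 | Consistency, s = 80 | Absolute, s = 60 | Absolute, s = 80 |
|---|---|---|---|---|
| 0 | 3600/3676.9 = 0.979 | 6400/6476.9 = 0.988 | 0.979 | 0.988 |
| 20 | 0.979 | 0.988 | 3600/3876.9 = 0.93 | 6400/6676.9 = 0.96 |
| 40 | 0.979 | 0.988 | 3600/4476.9 = 0.80 | 6400/7276.9 = 0.88 |
| 60 | 0.979 | 0.988 | 3600/5476.9 = 0.66 | 6400/8276.9 = 0.77 |

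Simulation at n = 100 agrees to within about 0.002. The consistency form does not move. The absolute form does, but by an amount that also depends on s, and a reader cannot recover b or its sign from it.

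**3. Sensitivity to two modelling choices.**

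- *Recording length.* The table lets device TST exceed the time recorded. With TST capped at an assumed 480 min, simulation at b = 60 gives a consistency ICC of about 0.95 and an absolute-agreement ICC of 0.64 to 0.75; the mean error itself falls to about 52 to 55 min.
- *Bias that grows with wake time.* If the bias is (b/120) × (480 − TST), the SD of the difference is √[(b·s/120)² + 12.4²]. At b = 20, s = 60 this is √(10² + 12.4²) = 15.9 min; at b = 60, s = 80 it is √(40² + 12.4²) = 41.9 min. Any such pattern implies a difference SD above the plan's 12.4. At a mean bias of 40 min the consistency ICC is then about 0.90 to 0.91 and the absolute form 0.69 to 0.77.

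**4. Whether the epoch tables fill the gap.** Section 2.3 notes of PSG that "Data are often scored visually, in 30-second epochs". If device and PSG epochs were aligned at that length, the pooled Wake/Sleep table would give the signed mean error: (wake scored as sleep − sleep scored as wake) × 0.5 min / n. Pooling discards which patient each epoch came from, so the table cannot show how the TST error varies between participants. Nor does section 4.3 say that it will be used for TST.

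**5. What limits of agreement would add.** At SD 12.4 they lie 1.96 × 12.4 = 24.3 min either side of the mean. The SE of each limit is 12.4 × √(1/100 + 1.96²/198) = 2.13 min, so each is estimated to about ±4.2 min.

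**The case against.** The strongest reply is that the estimate is already in the plan. Sections 4.2 and 4.3 belong to the same statistical chapter, and 4.2 names both the TST difference and its interval. Read as a whole, the chapter may lack only a cross-reference. Section 4.4 also says that the detailed plan is still to come, so 4.3 need not be an exhaustive list. And nothing is lost for good: an ICC for TST needs each participant's paired values, from which the difference can be computed.

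Much of this stands. It rules out the reading that the investigators do not intend to report a TST difference, or that they have chosen the ICC as their primary analysis; no section says either. It does not remove the gap: the analysis section is where the primary analysis should be named, and the later plan is neither in the documents nor due before data are examined.

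Three further inferences go too far:

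- A reader might conclude that the pooled epochs would give a falsely narrow CI for TST. The plan uses them for agreement, accuracy and kappa statistics and never proposes such an interval.
- A reader might say that an absolute-agreement ICC cannot tell over- from underestimation. Its value is the same for either sign only when the bias is constant. With bias proportional to wake time, +40 and −40 min give 0.69 and 0.82 (TST SD 60) or 0.77 and 0.87 (SD 80). The accurate statement is that the ICC does not report the sign.
- Limits of agreement are good practice, but no section promises them, so their absence is not a contradiction.

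**Conclusion.** The point holds as a should-fix. Section 4.3 does not carry through the estimate that section 4.2 announces, and the one statistic it assigns to TST is not specified well enough to be reproduced. This follows from the text alone, with no assumption.

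The size of the consequence is illustrative. It rests on an assumed PSG TST mean of 360 min and SD of 60 to 80 min, on assumed biases up to 60 min, and on using 12.4 min as residual SD. Under those assumptions a constant 60-minute error is invisible to an uncapped consistency ICC (0.98 to 0.99), barely visible once TST is capped at 480 min (about 0.95), and lowers an absolute-agreement ICC to 0.66 to 0.77 without showing minutes or direction.

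A reader might infer that the sample size is wrong or that the primary objective cannot be met. Neither follows: the ±2.5 min reproduces from the plan's own inputs, and the data needed will be collected.

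**What to change.** Amend section 4.3 before the 10-per-device data review:

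1. Name as the primary analysis, for each device, the mean paired device-minus-PSG TST difference with its 95% CI, computed over participants, as section 4.2 anticipates.
2. Add 95% limits of agreement, and a plot or check of the difference against TST. If the difference changes with TST, report that alongside the mean.
3. Keep the ICC as supportive, specified as two-way, single-measure, absolute agreement.

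The cost is a little more analysis on the same data, with no change to sample size, procedures or data collection. The real downside is presentational: bias and limits in minutes may look less favourable to a device than an ICC alone.

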#### 4.4 Study Monitoring

The investigators will follow weekly accrual statistics including number of participants approached for participants, proportion giving consent, and reasons for refusal. We expect 20-30 participants to enroll per week. We expect to complete accrual in mid-2016.

We are not planning formal interim analyses. We will perform interim evaluation of study data after 10 participants have worn each device to assure that there are no issues with data transfer and to develop the detailed analysis plan. We do not expect any adverse events related to study participation. The investigators will review the occurrence of any device related adverse events. An outside review may be convened if the investigators are concerned about the occurrence of adverse events.

